## **STATISTICAL ANALYSIS**

The statistical analysis will be conducted with the help of Spss software.

Continuous variables are presented through descriptive statistics, including mean, median, variance, minimum and maximum value. Categorical variables are described by the absolute frequencies and percentages.

Data will be examined by T-test or one-way ANOVA (normally distributed variable), Mann-Whitney U test, Kruskal-Wallis one way analysis test (not normally distributed variables), Pearson or Mc Nemar's chi-square test (categorical variables) will be used to evaluate the difference across non-AKI group versus AKI group according to KDIGO criteria or each type of AKI. Two-sided p-values of less than 0,05 were accepted as statistically significant.

Logistic regression analysis will used to build a model of covariates associated with development of AKI and risk of AKI. Likelihood ratio (LR) test statistic, Hosmer-Lemeshow (HL) statistic will used

for assessing goodness of fit (GOF) in the regression models. A discriminatory performance [DP] assessment of the binary logistic model will be performed by classification/diagnostic table, ROC and area under the curve (AUC).

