## **SECONDARY ENDPOINTS**

- Distinction between transient and persistent AKI
- Occurrence of recovery or progression at 7 days, 30 days and 3 months
- Association between AKI and pulmonary complications, major adverse cardiovascular events, anastomotic or septic complications, or death.
- Identify risk factors associated with AKI occurrence.

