### **Assessment of complications and mortality**

Postoperative pulmonary complications were identified and categorized based on European Perioperative Clinical Outcome (EPCO) definitions from the ESA-ESICM joint taskforce on perioperative outcome measures. These include respiratory infection, respiratory failure, pleural effusion, atelectasis, pneumothorax, bronchospasm, aspiration pneumonitis.

Major adverse cardiac and cerebrovascular events (MACCE) was a composite outcome of non-fatal cardiac arrest, acute myocardial infarction, congestive heart failure, new cardiac arrhythmia, angina, ischemic stroke.

Sepsis was defined according Sepsis-3 definition.

We performed separate analyses of complications apparently related to surgical technique (for instance, anastomotic leakage, fistula, abscess, hemorrhage) and medical complications, i.e. pulmonary, cardiovascular (acute myocardial infarction, atrial fibrillation, cardiogenic shock) and septic.

All complications were evaluated 30 days after surgery.

Mortality in hospital after resection of esophageal cancer was defined as any death during the admission when the operation was performed. This was more reliably quantified than 30-day mortality.

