### COMORBIDITIES:

- COPD Gold class \_\_\_\_
- Interstitial Lung Disease
- pulmonary hypertension
- asthma
- active smokers
- dyspnea
- stroke/TIA
- coronary artery disease
- DM
- hypertension with medication
- active solid organ neoplasm
- hematologic neoplasm
- disseminated cancer
- alcohol use disorder
- dementia
- congestive heart failure in 30 days prior to surgery
- dialysis
- ascites within 30 days prior to surgery
- systemic sepsis within 48 hours prior to surgery
- ventilator dependent

ASA class \_\_\_\_\_

Functional status: Karnofsky \_\_\_\_\_ ECOG \_\_\_\_\_

Weight loss within the last 3 months \_\_\_\_\_

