**Outcomes:**

need for RRT: \_\_\_\_\_days

MACCE within 30 days:  AMI

congestive heart failure

non-fatal cardiac arrest

new cardiac arrhythmia

angina

stroke

pulmonary complications within 30 days:  respiratory infection at \_\_\_\_day (i.e. patients has received antibiotics for a suspected respiratory infection + one of the following: new or changed sputum, new or changed opacities, fever, wbc >12000)

respiratory failure at \_\_\_\_day (PaO2 < 60 mmHg at room air, a P/F < 300 mmHg or SpO2 <90% requiring oxygen therapy)

pleural effusion at \_\_\_\_day

atelectasis at \_\_\_\_day

pneumothorax at \_\_\_\_day

bronchospasm at \_\_\_\_day (bronchodilators treatment for new expiratory wheezing)

aspiration pneumonitis at \_\_\_\_day

length of CMV \_\_\_\_h

need for NIV in \_\_\_\_\_h

surgical complications within 30 days:  fistula       hemorrhage       abscess

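### McNemar's paired test is offered for comparing AKI with non-AKI patients, who are unpaired, and the case report form has no postoperative sepsis item and no named anastomotic leakage item

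*Combined protocol and SAP*

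**What the plan says.** For categorical variables, the Statistical Analysis section of the combined protocol and SAP says: "Pearson or Mc Nemar's chi-square test (categorical variables) will be used to evaluate the difference across non-AKI group versus AKI group". The sentence goes on to include comparisons by type of AKI. It gives no rule for choosing between the two tests, does not reserve McNemar for repeated measurements, and no section describes matching.

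The Secondary Endpoints section lists: "Association between AKI and pulmonary complications, major adverse cardiovascular events, anastomotic or septic complications, or death".

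Under Assessment of complications and mortality, the methods say "Sepsis was defined according Sepsis-3 definition", name septic events as a category of medical complication, and give as examples of technique-related complications "anastomotic leakage, fistula, abscess, hemorrhage", so leakage and fistula appear as separate items.

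In the case report form, the only sepsis entry is a comorbidity, "systemic sepsis within 48 hours prior to surgery". The Outcomes page has three complication blocks: "MACCE within 30 days", "pulmonary complications within 30 days" and "surgical complications within 30 days". The last of these offers fistula, hemorrhage and abscess. Each pulmonary complication has a day field; the cardiovascular and surgical items do not.

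**The concern.** McNemar's test needs paired observations. Each patient here is either in the AKI group or in the non-AKI group, and nobody in one group is paired with anybody in the other. Software will still run the test on the two-by-two table of AKI (yes/no) by complication (yes/no), because those are two binary variables on the same patient. What it then tests is whether the proportion with AKI equals the proportion with the complication. That is not the association named in the endpoint. A p-value from it could suggest an association that is absent or miss one that is present.

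The data-capture gap does not depend on which test is chosen. An outcome that is defined in the methods but has no field on the form may not be abstracted, or may be abstracted inconsistently. The association of AKI with septic complications could then not be analysed as defined, and the one with anastomotic complications would depend on how each abstractor reads fistula.

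**Working it through.** **The plan's own figure.** Sample Size: 8 covariates × 8 events = 64 outcome events. This reproduces and is not in dispute.

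**Illustrative study size.** The plan fixes no total; it is to follow from a pilot of 100 patients. I take 64 AKI events and an AKI incidence cited in the Introduction:
- 18.3%: 64 / 0.183 = 349.7, about 350
- 11.9%: 64 / 0.119 = 537.8, about 538
- 35.3%: 64 / 0.353 = 181.3, about 181

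Complication rates are assumptions, because the documents set none for this study.

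**Formulas.** Let a = AKI with complication, b = AKI without, c = no AKI with complication, d = neither.
- Pearson: n(ad − bc)² / [(a+b)(c+d)(a+c)(b+d)]
- McNemar: (b − c)² / (b + c)

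Since b − c = (a+b) − (a+c), McNemar compares the number with AKI to the number with the complication.

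**No association, unequal frequencies.** 19/64 (29.7%) versus 86/286 (30.1%), so a, b, c, d = 19, 45, 86, 200.
- Pearson: 350 × (3800 − 3870)² / (64 × 286 × 105 × 245) = 0.0036, p = 0.95
- McNemar: (45 − 86)² / 131 = 12.83, p = 0.0003

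**Strong association, equal frequencies.** 32/64 (50.0%) versus 32/286 (11.2%), odds ratio (32 × 254)/(32 × 32) = 7.9.
- Pearson: 350 × (8128 − 1024)² / (64 × 286)² = 52.7, p = 4 × 10⁻¹³
- McNemar: (32 − 32)² / 64 = 0, p = 1.00

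**Simulated rejection with no association** (two-sided 5%, 200,000 studies per setting, AKI count free to vary):

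| AKI rate, n | 10% | 15% | 20% | 25% | 30% |
|---|---|---|---|---|---|
| 18.3%, 350: McNemar | 89% | 22% | 9% | 58% | 95% |
| 11.9%, 538: McNemar | 17% | 32% | 95% | 100% | 100% |
| 35.3%, 181: McNemar | 100% | 99.5% | 91% | 57% | 19% |

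Columns are complication rates. Pearson stays at 4.8 to 5.2% throughout. McNemar is near 5% only when the complication is about as common as AKI: at n = 350 with both at 18.3% it rejects in 5.1%.

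**Power.** At n = 350 with a true odds ratio of 3 (risks 34.2% versus 14.7%) and both frequencies 18.3%, McNemar rejects in 5% of studies and Pearson in 92%.

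**Form against methods.**

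| Outcome in endpoints or methods | Field on the case report form |
|---|---|
| Pulmonary | Seven complications, each with a day |
| Cardiovascular | Six items, no day |
| Sepsis (Sepsis-3) | None after surgery; one preoperative comorbidity |
| Anastomotic leakage | None by that name |
| Fistula, abscess, hemorrhage | Present, no day |
| Death | At ICU discharge, hospital discharge and 30 days |

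The complication grading on the form names neither sepsis nor leakage.

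**The case against.** The strongest reply is that the sentence is a loosely worded menu of tests by data type. Pearson is named first and is valid, and a competent analyst would use it. The study also has a natural place for a paired test: renal status in the same patients at 7 days, 30 days and 3 months. All of this stands. It makes the McNemar figures conditional on that test being chosen; it does not make the wording right, because the text assigns the test to the between-group comparison and not to the repeated one.

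On the form, fistula may be meant to cover leakage, and abscess or respiratory infection will capture some infections. The first is plausible, which is why a clarifying statement would be enough. The second does not supply Sepsis-3 sepsis.

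A reader might go further in ways the documents do not support:
- **That the association endpoint cannot be analysed without onset days for cardiovascular and surgical events.** The endpoint asks only for association, and the methods assess complications at 30 days, so it can be tested without them.
- **That such events cannot be ordered against AKI at all.** The postoperative table has serial troponin, BNP, hemoglobin, drainage and vasoactive drug entries, which give partial timing for some events where recorded.
- **That unadjusted tests, or in-hospital death as the mortality measure, are errors.** The plan promises association, not an independent or causal effect; it gives its reason for in-hospital death, and the form already collects 30-day death. Adjusted models or additional mortality reporting would be preferences.

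**Conclusion.** Two corrections are warranted, both confined to secondary endpoints.

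First, McNemar is not valid for AKI versus non-AKI. If it were used, the false-positive rate in the settings examined would run from about 5% to 100%, depending on how far the complication rate lies from the AKI rate, and a real association could be missed when the two are similar. These sizes rest on the assumed totals (64 AKI events at the cited incidences) and on assumed complication rates. The fault itself rests on neither. It would be wrong to infer that the association analyses are already compromised, since the plan equally permits the valid test.

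Second, the form as printed has no field for postoperative sepsis, which the methods define as an outcome, and is ambiguous about anastomotic leakage. The sepsis gap is clear; the leakage gap may be only one of labelling. No size can be put on the events that would be lost.

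The primary endpoint, AKI incidence within 48 hours, and the AKI risk-factor model are unaffected.

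**What to change.** 1. **Statistical Analysis.** For AKI versus non-AKI, and for comparisons between types of AKI, specify Pearson's chi-square test, or Fisher's exact test when an expected count is below 5. With 64 AKI patients in 350, the smallest expected count for an uncommon complication is 64 × its rate, so Fisher applies below 5/64 = 7.8%. Keep McNemar only if it is tied to a named within-patient comparison, such as renal status at two time points.
2. **Case report form, Outcomes page, before abstraction.** Add a postoperative sepsis item (Sepsis-3, within 30 days). Add an anastomotic leakage item, or state that fistula includes leakage.
3. **Optional.** Record onset days for sepsis, cardiovascular and surgical complications, as is already done for pulmonary events, so that their order relative to AKI can be described. The endpoint as written does not require this.

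The cost is one clause in the analysis text, a few extra fields and a little more chart review. If abstraction has already begun, the charts already abstracted would have to be reopened for the new items.

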## **AIM OF THE STUDY**

The aim of this study is to evaluate the incidence of postoperative AKI in patients undergoing elective esophageal cancer surgery. Secondary, we will assess the progression of the acute injury and the association with adverse pulmonary, cardiac, anastomotic, and septic events, as well as mortality. We will also identify risk factors associated with AKI occurrence.

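### The secondary endpoint linking AKI to complications and death has only unadjusted comparisons; no adjusted model is specified for it, and McNemar's paired test is listed for independent groups

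*Combined protocol and SAP*

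**What the plan says.** The Aim of the Study section sets out to assess "the association with adverse pulmonary, cardiac, anastomotic, and septic events, as well as mortality". The Secondary Endpoints section repeats this as "Association between AKI and pulmonary complications, major adverse cardiovascular events, anastomotic or septic complications, or death", and lists risk factors for AKI as a separate item. In the first item AKI is the exposure; in the second it is the outcome.

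The Statistical Analysis section gives two kinds of method:

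- Group comparisons by t-test, ANOVA, rank tests and, for categorical data, "Pearson or Mc Nemar's chi-square test (categorical variables) will be used to evaluate the difference across non-AKI group versus AKI group", or across the types of AKI.
- A regression: "Logistic regression analysis will used to build a model of covariates associated with development of AKI and risk of AKI". Its fit statistics are described as being "for assessing goodness of fit (GOF) in the regression models", in the plural, but no second model is described.

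The Sample Size section refers to one final multivariable model and asks for about 64 outcome events for 8 covariates. It does not name the outcome.

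The section on complications and mortality adds: "We performed separate analyses of complications apparently related to surgical technique", with medical complications analysed apart from these. It gives no method. It also says: "All complications were evaluated 30 days after surgery".

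**The concern.** The two secondary questions need different models, and the plan describes a model for only one of them. Patients who develop AKI differ from those who do not. The plan expects this, because it sets out to find risk factors for AKI. Any such factor that also raises the risk of a complication or of death will produce a crude association even if AKI itself plays no part. A reader of the results could not tell whether a reported link reflects AKI, a sicker patient or a harder operation. If covariates are chosen only after the data have been seen, the adjusted result will also depend on that choice.

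A smaller matter is McNemar's test. It is for paired observations, and AKI and non-AKI patients are different people; no matching is described. Applied to an AKI-by-complication table, it asks whether the two events are equally common, not whether they are associated.

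**Working it through.** **The plan's own figure.** 8 covariates × 8 events per covariate = 64 events, as stated.

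**Matching endpoints to methods.**

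| Secondary question | Role of AKI | Stated test | Stated model |
|---|---|---|---|
| Risk factors for AKI | outcome | group comparisons | logistic regression |
| Complications, death | exposure | group comparisons | none named |

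No section describes a model with a complication or death as dependent variable, a confounder set for one, matching, stratification or a propensity score.

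**Illustration of confounding. All confounder inputs are assumed.** Take one binary confounder with prevalence q, baseline AKI risk 12%, baseline complication risk 20%, the same odds ratio on both, and no effect of AKI. The crude odds ratio is (both × neither) / (AKI only × complication only), with each cell averaged over the two confounder strata.

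Worked case, odds ratio 4 and q = 40%:

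- AKI risk with the confounder: odds 0.12/0.88 × 4 = 0.545, so 35.3%. Complication risk: odds 0.25 × 4 = 1, so 50%.
- Both: 0.6×0.12×0.20 + 0.4×0.353×0.50 = 0.0850
- AKI only: 0.6×0.12×0.80 + 0.4×0.353×0.50 = 0.1282
- Complication only: 0.6×0.88×0.20 + 0.4×0.647×0.50 = 0.2350
- Neither: 0.6×0.88×0.80 + 0.4×0.647×0.50 = 0.5518
- Crude odds ratio = (0.0850 × 0.5518)/(0.1282 × 0.2350) = 1.56, where the true value is 1.

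| q | OR 2 | OR 3 | OR 4 |
|---|---|---|---|
| 20% | 1.10 | 1.28 | 1.49 |
| 40% | 1.13 | 1.33 | 1.56 |
| 60% | 1.11 | 1.27 | 1.44 |

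**False-positive rate.** This depends on n, which the plan leaves to a 100-patient pilot. For scale, 64 events at three of the incidences cited in the Introduction give 64/0.353 = 181, 64/0.183 = 350 and 64/0.119 = 538 patients (the lowest, 2.4%, gives 2,667). In the worked case, simulated two-sided Pearson tests at 0.05 reject in about 23%, 38% and 53% of cohorts of 181, 350 and 538. At odds ratio 2 and n = 350 the rate is only 6–7%. The AKI rate in the worked case is 21.3%, so these values of n serve as plausible cohort sizes and do not yield exactly 64 events.

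**McNemar on invented tables, 64 AKI patients of 350.** Cells are AKI with and without the complication, then non-AKI with and without it.

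- 19/45/86/200, about 30% in both groups. McNemar: (45−86)²/(45+86) = 12.83, p = 0.0003. Pearson: 0.004, p = 0.95.
- 24/40/40/246, 37.5% against 14.0%, odds ratio 24×246/(40×40) = 3.69. McNemar: (40−40)²/80 = 0, p = 1.0. Pearson: 19.35, p = 0.00001.

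**Room for adjustment.** At the plan's ratio of 8 events per covariate and an assumed n = 350, an outcome risk of 3%, 5%, 10% or 30% gives 10.5, 17.5, 35 or 105 events. That allows 1, 2, 4 or 13 covariates, AKI included. The outcome risks are assumptions; the documents give no planning rate.

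**The case against.** The plan promises an association, not an independent or causal effect, and a crude comparison does address an association. This stands: the plan does not contradict itself, and the gap is one of specification in one secondary endpoint.

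The unnamed outcome in the Sample Size section and the plural in "for assessing goodness of fit (GOF) in the regression models" leave room for further models. This also stands in part. A reader might infer that the plan rules out adjustment, and the text does not support that. Equally, neither phrase names a complication or death as an outcome, so neither supplies the missing model.

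On McNemar, the sentence is a generic list with Pearson's test named first. The plan also follows recovery at 7 days, 30 days and 3 months, where a paired test could be valid within patients. A reader might infer that the association analyses will be invalid. That does not follow, because the correct test is offered as the alternative. The wording nevertheless attaches McNemar to the comparison between groups.

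Finally, the numerical illustrations rest on assumed confounders and on sample sizes that the plan never states. This is correct; they show how the distortion arises and how it varies.

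**Conclusion.** The point holds as a gap in specification. AKI as exposure for complications and death is a stated secondary endpoint. Its only stated analyses are unadjusted, and the only regression with an identifiable outcome has AKI as that outcome.

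The size of the bias in this cohort cannot be derived from the documents. Under the assumptions shown, it is small for a confounder of odds ratio 2 and material at 3 to 4. It would be wrong to infer that any reported association must be spurious, or to attach one false-positive rate to this study. The McNemar reference is a minor wording error and would not justify this point alone. The change should be made, but the primary incidence endpoint does not depend on it.

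**What to change.** 1. For each complication group in the secondary endpoint and for death, report the AKI odds ratio with 95% CI, both crude and adjusted. Adjust for a short prespecified list of preoperative and intraoperative variables already on the case report form, for example age, ASA class, baseline eGFR and blood loss. Limit the number of covariates by the events of that outcome, and label the estimate as unadjusted where events are too few.
2. State in the Sample Size and Statistical Analysis sections which outcome each multivariable model has.
3. Delete McNemar's test for AKI against non-AKI. Use Pearson's test, or Fisher's exact test when expected counts are small.
4. Report the results as associations.

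**Cost.** Protocol wording, a few extra models and somewhat wider intervals. The covariates need no new fields.

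**Limits.** The Outcomes part of the case report form has no field for postoperative sepsis, so the septic outcome can be analysed only if it is captured. Death may allow little or no adjustment. Adjustment does not settle whether AKI or the complication came first: complications are counted over 30 days without requiring onset after AKI. The form records a day for pulmonary complications but none for cardiovascular events or under "surgical complications within 30 days".

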## INTRODUCTION

Surgery alone, or in combination with neoadjuvant chemoradiation therapy, is still considered to be the cornerstone treatment for locally advanced esophageal cancer . Esophagectomy serves as an exemplar of major operative trauma, with well-known risk of pulmonary, cardiac, anastomotic, and septic complications and the presence of postoperative complications after esophagectomies for cancer is associated with a reduced long-term survival . There is a paucity in the literature regarding postoperative renal outcomes after esophageal surgery, with a wide range of incidence.

McCulloch et al  reported in 2003 the results of the British ASCOT prospective database collecting data from 955 patients (ASA score of 3-4 in 25%), of whom 229 underwent esophageal surgery. They found an incidence of renal complications of 3.5%, but no definition of renal complication was present in the study.

Lee et al  in 2014 investigated retrospectively 595 patients underwent esophageal surgery for cancer in South Korea. AKI according AKIN criteria was found in 35.3% of the population with a mean age of 62 years and mainly ASA score 2 (91.8%). AKI was also associated with longer hospital stay.

Moore et al  compared in a retrospective analysis of 150 patients underwent complex or non-complex esophageal reconstruction in 2016, reporting an incidence of renal insufficiency in 1.3% of the entire population, without reference of any diagnostic criteria.

In 2017 Konda et al  performed a retrospective study on 897 patients with a mean age of 61 years and mainly ASA 3 (83.6%) in USA, of whom 11.9% fulfilled the AKIN criteria for AKI.

Wang et al  showed in a Chinese retrospective case-control study published in 2017 a very low incidence of AKI according RIFLE criteria (2.4%) in a population of 2094 patients with a median age of 62 years and with ASA score of 2 in 84% of the patients.

The most recent study by Murphy et al  published in 2020 on 1135 patients with a mean age of 64 years underwent esophageal cancer surgery in three high-volume centers in Ireland showed an incidence of AKI (defined by AKIN criteria) of 18.3%, associated with atrial fibrillation and longer hospital stay.

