## **SAMPLE SIZE**

Our sample size will be determined to help ensure stability around the point estimates in the final multivariable model. To avoid overfitting our final outcome model, no more than 8 outcome events will be required per covariate of interest. Thus, to fit a model with 8 covariates, we will require approximately 64 outcome events. We will estimate the sample size after a pilot study on 100 patients.

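### The AUC and classification table for the AKI risk-factor model are planned with no described validation, so they would be modestly optimistic (AUC by about 0.03–0.09 under stated assumptions)

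*Combined protocol and SAP*

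**What the plan says.** The model serves the last of the listed secondary endpoints, "Identify risk factors associated with AKI occurrence". In the Statistical Analysis section, "Logistic regression analysis will used to build a model of covariates associated with development of AKI and risk of AKI". No covariates are listed there and no selection rule is given.

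Two sets of checks follow. For fit, "Likelihood ratio (LR) test statistic, Hosmer-Lemeshow (HL) statistic will used", with the stated purpose "for assessing goodness of fit (GOF) in the regression models". For discrimination, "assessment of the binary logistic model will be performed by classification/diagnostic table, ROC and area under the curve (AUC".

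The Sample Size section contains the only safeguard against overfitting: "To avoid overfitting our final outcome model, no more than 8 outcome events will be required per covariate of interest". It continues: "Thus, to fit a model with 8 covariates, we will require approximately 64 outcome events". The total number of patients is to be set after a pilot of 100, which is given no validation role. The study population comes from a single hospital.

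**The concern.** A logistic model fitted by maximum likelihood is tuned to the patients it was fitted on. Its AUC, ROC curve and classification table in those same patients therefore look better, on average, than they would in other patients from the same population. The plan recognises overfitting when it sets the number of events. It then reports performance by measures that contain whatever overfitting remains, and names no step to estimate or remove it.

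The AUC and classification table are the plan's only stated measures of how well the model separates AKI from non-AKI patients. If they are published as apparent values, a reader cannot tell how much of the figure is optimism.

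**Working it through.** **The plan's own figure.** Events = events per covariate × covariates = 8 × 8 = 64, which matches Sample Size. The documents give no AUC and no final number of patients, so the size of the optimism has to be simulated.

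**Inputs from the documents.** 8 covariates; about 64 events; three of the AKI incidences cited in the Introduction (11.9%, 18.3%, 35.3%; for the middle one, the study that "showed an incidence of AKI (defined by AKIN criteria) of 18.3"%). Patients needed = 64 / incidence, rounded up:
- 64 / 0.119 → 538
- 64 / 0.183 → 350
- 64 / 0.353 → 182

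**Assumptions, not in the documents.** Eight independent pre-specified single-term covariates (4 binary at 30%, 4 normal), all in the model, with an equal log odds ratio per SD of 0, 0.15, 0.25 or 0.40. The three non-zero values correspond to a true AUC of about 0.62, 0.69 and 0.77. There were 1,000 replicates per setting, each tested on 4,000 new patients.

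**Optimism = apparent AUC − new-patient AUC.**

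| True AUC | n = 538 | n = 350 | n = 182 |
|---|---|---|---|
| 0.50 (no signal) | 0.604 − 0.500 = 0.104 | 0.608 − 0.500 = 0.108 | 0.621 − 0.500 = 0.121 |
| 0.62 | 0.654 − 0.588 = 0.066 | 0.656 − 0.587 = 0.069 | 0.667 − 0.580 = 0.087 |
| 0.69 | 0.713 − 0.670 = 0.043 | 0.712 − 0.665 = 0.047 | 0.715 − 0.654 = 0.061 |
| 0.77 | 0.791 − 0.765 = 0.026 | 0.790 − 0.757 = 0.033 | 0.787 − 0.744 = 0.043 |

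Over the nine settings with real effects the range is 0.026 to 0.087, or about 0.03–0.09. A separate simulation with eight normal covariates gave 0.045 at n = 350 and a true AUC of 0.70 (0.723 against 0.678).

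**Apparent AUC − true AUC of the covariates.** This is a smaller gap. In the table it runs from 0.787 − 0.77 = 0.017 to 0.667 − 0.62 = 0.047. Because the true AUCs are rounded and vary a little with incidence, read this as about 0.01–0.05.

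**Calibration and classification (n = 350, true AUC 0.69).**
- The calibration slope is 1.00 in the fitting data by construction, and 0.76 in new patients.
- The plan names no cut-off, so two were tried. At the observed incidence, sensitivity falls from 0.650 to 0.588 and specificity from 0.662 to 0.648. At the best point on the ROC curve, sensitivity falls from 0.675 to 0.561 and specificity from 0.688 to 0.665.

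**What the planned checks show.**
- Hosmer-Lemeshow (10 groups, 5% level) rejects in 3.7%–6.1% of datasets over all 12 settings, about its nominal rate whatever the optimism.
- The LR test at n = 350 rejects in 5.9%, 55.2%, 96.4% and 100% of datasets as the effects grow. It is non-significant in 100 − 5.9 = 94.1% of no-signal datasets and in 100 − 55.2 = 44.8% of weak-signal ones.

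**What is not materially affected (2,000 replicates).** At log odds ratio 0.25, bias is +2.2%, +3.2% and +5.9% at n = 538, 350 and 182. Coverage of the 95% interval, with and without real effects, is 94.6%–95.1%. The false-positive rate per null covariate is 4.9%–5.4%.

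**Does the remedy work?** In 300 replicates with 100 bootstrap resamples each (n = 350, true AUC 0.69), the mean apparent AUC of 0.716 was corrected to 0.673, against 0.665 in new patients. The corrected value was the closer one in 80% of datasets. With no signal, 0.606 was corrected to 0.531, against 0.500.

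**The case against.** **The aim is to find risk factors, not to build a prediction tool.** No section plans a risk score or use of the equation in new patients. On that view the relevant gap is between the apparent AUC and the covariates' true AUC, only about 0.01–0.05. This stands and lowers the severity. It does not remove the point, because the plan chooses to report AUC and classification, and both gaps run upward.

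**Sampling error is larger than the bias.** With A = 0.69, 64 events and 286 non-events, the Hanley-McNeil variance is [A(1−A) + 63(A/(2−A) − A²) + 285(2A²/(1+A) − A²)] / (64 × 286). The SE is about 0.039 and the 95% half-width 1.96 × 0.039 ≈ 0.08. That is useful for scale, but a confidence interval around an apparent AUC does not correct its centre.

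**The LR test gives some warning.** It does, in most no-signal datasets and nearly half of the weak-signal ones. So it would be wrong to say that nothing planned could raise doubt; what is missing is a measure of the optimism. Nor is it a fault that Hosmer-Lemeshow does not detect optimism, since the plan assigns it to goodness of fit only.

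**Computation on the fitting patients is inferred from silence.** True, but the documents describe no other patients on whom performance could be assessed.

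**Stronger readings that a reader might infer.**
- *The eight covariates will be picked from the many items on the case report form.* If 8 were chosen from 20 to 50 candidates, a simulation at a true AUC of 0.70 gives optimism of about 0.08–0.15. The documents do not say that this will be done, so the point does not rest on it.
- *The risk-factor results are unsound.* With pre-specified covariates the odds ratios and their tests hold up well.
- *The events rule sets a ceiling, so fewer events would do.* The wording allows this, but the stated purpose and the 64-event figure show that a minimum is meant.

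**Conclusion.** The point holds as a minor to moderate one. The documents describe no internal or external validation, so the planned AUC and classification table would be apparent figures, biased upward. Under the stated assumptions the excess over new-patient AUC is about 0.03–0.09, and about 0.05 in the central case. It would be larger if covariates were selected from the data.

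These sizes depend on assumed effects, independent covariates and about 64 events. They are not estimates for this cohort, whose size and AUC are not yet known. The consequence, with pre-specified covariates, is confined to the reported performance of a secondary model. The primary incidence estimate is not touched.

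**What to change.** In Statistical Analysis, add after the sentence on discrimination:

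> The apparent AUC and classification table will be reported beside bootstrap optimism-corrected AUC, sensitivity, specificity and calibration slope (for example 500 resamples), repeating any variable selection and cut-off choice in each resample.

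The cost is one sentence and a short script, possibly run outside SPSS, the only software the plan names. No extra patients or data are needed. The reported AUC will be lower, by about 0.05 in the central case. A little optimism remains: 0.673 − 0.665 = 0.008 in the central bootstrap run, and 0.531 − 0.500 = 0.031 with no signal.

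As an incidental wording correction, the events rule in Sample Size should read as a minimum (at least 8 events per covariate). The 64-event figure does not change.
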